11.3.7 Efficacy

Changes in pain, disability and quality of life indices will be described in the baseline situation and at 3, 6 and 12 months of treatment, which will be compared as specified in 11.2.

The frequency and percentage of patients presenting signs of regeneration at 12 months of the different interventions, comparing the values as specified in 11.2.

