11.2 STATISTICAL METHOD USED

In all descriptive analyzes, categorical variables will be summarized using frequencies and category percentages. For the distributions of continuous variables, will present the mean and its Standard Deviation, the median and the 25th and 75th percentiles of the distribution, the number of cases, minimum and maximum value.

All hypothesis tests will be two-tailed, with a significance level of 5%. The The result of a hypothesis test will comprise the 95% Confidence Interval of the variable (s) analyzed. To calculate the statistical significance of the differences between the two groups, a normality analysis of the distribution will be carried out and compare the means using the double-tailed t-test or the Wilcoxon, depending on whether the population is Gaussian or not.

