11.2.1 Main objectives, main variables

- Evaluate the feasibility and safety of the use of allogeneic MSV injected into the disc space for the treatment of lumbar degenerative disc disease and pain and the disability it causes.

The variables that will be used to evaluate safety will be the AAG number related to study medication and the percentage of patients who presented a related AGS. -Evaluate the analgesic-anti-inflammatory efficacy determined by the variation of the Low back pain assessment questionnaire scores (VAS), disability (Oswestry) and health and quality of life (SF12) at 3, 6 and 12 months.

- Evaluate regenerative efficacy using quantitative MRI imaging criteria determined by the appearance of improvements in disc dehydration at 6 and 12 months.

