11.3.4 Analysis methods

Descriptive statistics will be made including summary statistics and lists. For the comparisons of means at 0, 6 and 12 months a comparison of means using the t-test or Wilcoxon test as appropriate (see 11.2).

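### The 12-month regeneration percentage is sent to a test on means; no test or usable interval for a difference in percentages is named

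*Combined protocol and SAP*

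**What the plan says.** Section 11.3.7 of the combined protocol and SAP sets this efficacy summary, as a count and a percentage of patients: "signs of regeneration at 12 months of the different interventions, comparing the values as specified in 11.2".

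The section it points to, 11.2, contains:
- For categorical variables, description only: "categorical variables will be summarized using frequencies and category percentages".
- For differences between the two groups, a normality check, after which the analyst will "compare the means using the double-tailed t-test or the Wilcoxon, depending on whether the population is Gaussian or not".
- For every test, a two-sided 5% level and an interval: the "result of a hypothesis test will comprise the 95% Confidence Interval of the" variable or variables analysed.

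The subsections of 11.2 add only paired Wilcoxon tests on disc height (11.2.1.1) and on the MRI quotient (11.2.1.2), each against the patient's own baseline. Section 11.3.4 repeats the t-test or Wilcoxon on means and refers back to 11.2. No test for a 2x2 table, and no interval for a proportion or a difference in proportions, is named anywhere.

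On safety, 11.2.1 lists "the percentage of patients who presented a related AGS" among the main variables. Section 11.3.6 asks for frequencies and percentages of serious and of all adverse events. It orders no test and no interval for them.

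**The concern.** The cross-reference joins a yes/no outcome to a rule written for continuous measurements. Three things follow.

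- The normality check has only one possible answer, since a 0/1 variable is not Gaussian. The rule leads to Wilcoxon.
- The test is not designed for a percentage. With 12 per arm, the choice of 2x2 method decides whether several plausible tables count as significant, so it should be fixed before the data are seen.
- The interval that 11.2 requires with each test cannot be obtained from Wilcoxon in a form that describes a difference in percentages. In a 24-patient trial that interval is the most informative result for this endpoint.

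**Working it through.** **Inputs.** 12 patients per arm (11.1); two-sided 5% (11.2); t-test or Wilcoxon on means (11.2). The plan gives no assumed rate, effect or power for this endpoint, so there is no planned figure to reproduce. The check enumerates all 13 x 13 = 169 possible results, a/12 v b/12.

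**Formulas.** Let m = a + b.
- Uncorrected chi-square: X² = 24(b - a)² / [m(24 - m)].
- Tie-corrected Wilcoxon, no continuity correction: z² = X² x 23/24.
- Pooled t on 22 df: t = (b - a)/12 divided by SE, where SE² = [a(12 - a) + b(12 - b)] / (12 x 11 x 12).
- True size at common rate p: the sum of Bin(a; 12, p) x Bin(b; 12, p) over the rejected tables.

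**Example, 3/12 v 8/12.** X² = 24 x 25/(11 x 13) = 4.196, above 3.841. z² = 4.196 x 23/24 = 4.021, p = 0.045. SE² = (27 + 32)/1584 = 0.0372, SE = 0.193, t = 0.4167/0.193 = 2.16, p = 0.042. All three reject.

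**Rejection regions.** Over all tables the t-test, the Wilcoxon and the uncorrected chi-square reject the same results. For 0/12 v 12/12 the t statistic is undefined and is counted as a rejection.

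**True size (nominal 5%)**

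| Common rate | t-test or Wilcoxon | Boschloo or Barnard | Fisher |
|---|---|---|---|
| 10% | 1.5% | 1.5% | 0.25% |
| 30% | 4.9% | 4.5% | 1.7% |
| 40% | 5.9% | 4.2% | 2.1% |
| 50% | 6.4% | 3.8% | 2.3% |
| Maximum, any rate | 6.4% | 4.5% | 2.3% |

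**Tables where the verdict depends on the test** (apart from swapping arms)

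| Result | t | Wilcoxon | Boschloo | Fisher |
|---|---|---|---|---|
| 0 v 4 and 8 v 12 | 0.028 | 0.032 | 0.045 | 0.093 |
| 1 v 6 and 6 v 11 | 0.024 | 0.028 | 0.029 | 0.069 |
| 2 v 7 and 5 v 10 | 0.036 | 0.039 | 0.042 | 0.089 |
| 3 v 8 and 4 v 9 | 0.042 | 0.045 | 0.064 | 0.0995 |

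Fisher reverses all eight patterns. Boschloo reverses only the last two, and so does Barnard.

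**Intervals**
- *Wilcoxon shift, 1/12 v 6/12.* The 144 pairwise differences are 6 x 11 = 66 at +1, 6 x 1 = 6 at -1 and 72 at 0. The median is 0 and the 95% interval is 0 to 1, although p = 0.028 and the observed difference is 5/12, or 42 points. Newcombe gives +5 to +67 points.
- *t-interval, 2/12 v 11/12.* SE² = (20 + 11)/1584 = 0.0196, SE = 0.140; 75 ± 2.074 x 14.0 gives +46 to +104 points. Newcombe gives +36 to +89.
- *t-interval, 0/12 v 0/12.* SE = 0 and the width is zero. Newcombe gives -24 to +24 points. This result has probability 0.95^24 = 29% if both true rates are 5%, and 0.90^24 = 8% if both are 10% (assumed rates).

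**Power, for illustration.** The rates are assumptions. Section 11.5 gives up to 30% for improvement under placebo and section 2.1 gives 71% of optimal effect in the autologous pilot; neither is a regeneration rate.

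| Assumed rates | Plan's rule | Boschloo or Barnard | Fisher |
|---|---|---|---|
| 30% v 71% | 59% | 48% | 41% |
| 30% v 60% | 36% | 27% | 21% |
| 10% v 50% | 60% | 59% | 42% |
| 30% v 80% | 77% | 68% | 61% |

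The plan's rule gains some of its power by exceeding 5% size at middling rates.

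**The case against.** The strongest reply is that little goes wrong in the testing. The plan's rule behaves as an uncorrected chi-square, is at or below 5% for common rates up to 30%, and never exceeds 6.4%. At a 50% rate, Fisher's 2.3% is further from nominal. This stands. A reader might infer from the eight patterns that the rule produces many false positives, but six of them remain significant under an exact unconditional test, so that list mainly shows Fisher's conservatism.

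The t-interval is also not hopeless. Its coverage at assumed rates of 30% v 60% is 94.2%, against 94.6% for Newcombe, and zero width needs both arms to be all-0 or all-1. This too stands. But the plan's own normality rule leads away from the t-test and to Wilcoxon, whose interval is uninformative here.

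The sentence in 11.3.7 is a translated fragment, and the values to be compared could be the continuous MRI quotients. That is possible. It does not rescue the percentage, which then has no method at all, and the test in 11.2.1.2 is paired within patients and cannot compare arms.

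A reader might also infer that the main safety percentage would be reported with a 0% to 0% interval if no related serious event occurred. The documents do not support this. Section 11.3.6 orders only frequencies and percentages, its reference to 11.2 concerns change from baseline in the laboratory parameters, and the interval in 11.2 is attached to hypothesis tests. The plan is silent on an interval there; it does not state a wrong one.

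**Conclusion.** The specification gap is real and cheap to close. The plan orders a comparison of a per-patient percentage by a rule for means and names no method for proportions.

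The effect on testing is modest: true size 1.5% to 6.4% for common rates of 10% to 50%, and two patterns with their mirror images whose verdict changes under an exact unconditional test. The effect on estimation is larger, because the required 95% CI is uninformative under Wilcoxon and can be out of range or of zero width under the t-test. The primary feasibility and safety objective is not compromised by this point. The change is advisable, but the trial does not depend on it.

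The figures assume 12 analysed patients in each arm. Section 11.3.2 restricts efficacy to a per-protocol set, so the actual denominators may be smaller and the exact tables would shift.

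**What to change.** In 11.2 and 11.3.7, state that the percentage with signs of regeneration at 12 months is compared between arms by one named exact unconditional 2x2 test (Boschloo or Barnard), two-sided at 5%, with a Newcombe 95% CI for the difference.

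Three details belong with it:
- Say that the test governs if the two disagree. For 3/12 v 8/12 Newcombe gives +2 to +67 points while p = 0.064.
- Define, per patient, what counts as a sign of regeneration. Sections 11.2.1.1 and 11.2.1.2 give only a direction of change, so the numerator is not yet fixed. State also how a missing 12-month MRI is counted.
- Confirm that the package named in 11.4 provides the chosen test and interval, or name one that does.

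Optionally, in 11.3.6, add Clopper-Pearson 95% CIs per arm for the serious and overall adverse event percentages. For 0/12 the upper limit is 1 - 0.025^(1/12) = 26.5%. This would be an addition, not a correction.

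Cost: a few sentences, and no change to any patient procedure. Against the plan's rule, nominal power in the illustrations falls by 1 to 11 points (59% to 48% at 30% v 71%). Fisher would cost more: 15 to 18 points, and in the 0/12 v 4/12 example p would move from 0.028 to 0.093.

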11.4 SOFTWARE

The statistical analysis will be carried out using the statistical package InStat (v.3.06. GraphPad

Software, Inc).

11.5. DIFFICULTIES AND LIMITATIONS OF THE STUDY

As noted above, previous clinical trials show that a considerable improvement (up to 30%) due to the placebo effect. It will therefore be accurate discount this random effect before assessing the effects of MSVs. It is therefore, important evolution in the control group.

Bone marrow donation could be a problem if not enough were found donors. The solution to be used, when possible, by patients undergoing treatment with autologous mesenchymals (in the trial we are conducting in collaboration with CM Teknon) also as allogeneic donors would be the situation ideal, the most economical in terms of required means and the most interesting scientifically.

We have tried to obtain the maximum masking in the test within a design reasonable for this first study. While the "single blind" (patient) design is feasible without serious complications, the "double blind" (researcher) or "triple" (analysis) various logistical and ethical issues, so they have been left for the future. If there are indications of efficacy for allogeneic MSV, it will not be possible to perform direct comparison with autologous MSVs, so if these are obtained results, a new trial should be designed to directly compare the efficacy of both therapeutic alternatives.

REFERENCES:

Adams MA, Dolan P & Hutton WC. (1986). The stages of disc degeneration as revealed by discograms. The Journal of bone and joint surgery 68, 36-41. Adams MA, Freeman BJ, Morrison HP, Nelson IW & Dolan P. (2000). Mechanical initiation of intervertebral disc degeneration. Spine (Phila Pa 1976) 25, 1625-1636. Aggarwal S & Pittenger MF. (2005). Human mesenchymal stem cells modulate allogeneic immune cell responses. Blood 105, 1815-1822.

Bernardo ME, Locatelli F & Fibbe WE. (2009). Mesenchymal stromal cells. Ann N Y Acad Sci 1176, 101-117.

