ANNEX VIII: MODIC CHANGES
ANNEX IX: RESEARCHER SIGNATURES PAGES A25
ANNEX X: INSURANCE POLICY
ANNEX XI: INSURANCE CERTIFICATE (Art.8; RD223 / 2004) A27

1. SUMMARY

Type of request:

Phase I-II, single-center, prospective, randomized, blinded ** and controlled clinical trial for the treatment of lumbar degenerative disc disease with allogeneic mesenchymal cells (MSV *), with two arms with 12 patients each. In the experimental arm, cells will be administered locally in the nucleus pulposus area of the affected segment "Ex Vivo" expanded allogeneic mesenchymal cells with the IBGM GMP procedure (MSV; PEI No. 10-134; authorized by the AEMPS). The control arm will infiltrate the area of the paravertebral musculature close to the injury with saline solution containing mepivacaine at 1% in the same volume and subject to the same maneuvers as the intervention on the arm experimental.

** Double blind, masked for the patient and evaluators performing the analysis of the results, open to the doctor who applies the cells.

Data relating to the Sponsor:

Citospin, Scientific Park of the University of Valladolid R + D Building, [name] NIF: NIF. B-47673538 Title of the clinical trial: Treatment of lumbar degenerative disc disease with allogeneic mesenchymal cells (MSV *). * MSV = Mesenchymal cells of the bone marrow prepared by the procedure of IBGM of Valladolid.

Protocol Code: Disc_allo_MSV Eudra-CT: 2012-004444-30

Experimental and control drug: dose, pharmaceutical form, route of administration, therapeutic group:

Experimental drug: The investigational drug or product is MSV, which is Mesenchymal bone marrow stromal cells obtained from healthy donors with negative serology (NAT; nucleic acid technology) and processed according to procedure of the IBGM (PEI Num. 10-134; approved by AEMPS), with the following characteristics: \Box Cell dose: 25x10e6 ± 5x10e6 MSV per disk.

□ Presentation: 2 ml of cell suspension in Ringer-lactate isotonic with 0.5% human albumin and 5 mM glucose in a 5 ml syringe. Stability:> 12 hours at 4-20 °C

□ Administration: Injection into the nucleus pulposus area of the affected disc

□ Therapeutic Group: Cell Therapy

Control drug: Injection of 2 ml of 1% mepivacaine in saline serum (see section 2.4). in the paravertebral musculature close to the injury, using the same volume and the same maneuvers as the intervention in the experimental arm.

Cell Production

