In the arm experimental mesenchymal cells obtained from healthy donors purified and expanded under GMP conditions using our protocol, authorized by the AEMPS (MSV, PEI No. 10-134). MSVs will infiltrate the affected intervertebral discs. Whenever possible (because there is sufficient material and explicit consent), use surplus cells from patients undergoing MSV therapy as donors autologous, which would significantly simplify the procedure. In the control arm it will infiltrate the area of the paravertebral musculature near the injury with saline solution containing 1% mepivacaine in the same volume and subject to the same maneuvers as the intervention in the experimental

arm. Study participants will be offered the possibility of receiving MSV treatment once the study is completed if it is demonstrated beneficial and the patient so wishes. The application of the cells will be carried out in the Valladolid University Clinical Hospital. The evaluation of the response to treatment will be blind and will be followed by the evolution of the indices of low back pain, disability and quality of life, as well as the improvement of the dehydration of the treated segments, quantified from magnetic resonance images (T2 sequence).

2.2. EPIDEMIOLOGY OF DEGENERATIVE DISC DISEASE. REPERCUSSION ECONOMIC AND SOCIAL.

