3.4. Secondary criteria

□ Clinical observations of the surgeon

□ Evaluation of lumbar pain and general health status according to the Visual Scale Analog (EVA, see Annex V). The score will be transformed to a scale 0-100% for analysis (Huskisson, 1974)

□ Disability assessment using the Oswestry questionnaire (Davidson & Keating, 2002) (ODI, see Annex VI).

□ Assessment of quality of life using the simplified version of the questionnaire Short Form-36 (Davidson & Keating, 2002). It has been shown that this simplification (SF-12; see Annex VII) has a statistical value that approximates much the complete test (Gandek et al., 1998).

4. TYPE OF CLINICAL TRIAL AND DESIGN OF THE SAME 4.1 Type of CT

Phase I-II clinical trial, single-center, prospective, randomized, blinded **, controlled for the treatment of lumbar degenerative disc disease with intact fibrous ring proven by MRI, with two arms: a control arm with placebo treatment (injection of mepivacaine at 1%) and another experimental arm treated with allogeneic MSV. This is the third application of a PEI consisting of Ex vivo expanded bone marrow mesenchymal cells (PEI No. 10-1349). In both cases, the product will be administered in a volume of 2 ml per injection in the nucleus pulposus area.

** Double blind, masked for the patient and evaluators performing the analysis of the results, open to the doctor who applies the cells.

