4.2 Overall study design

The study consists of 2 arms, one experimental with allogeneic MSV, and another control in the to be injected into the area of the paravertebral muscles near the injury saline serum containing 1% mepivacaine (1 ml of 2% mepivacaine + 1 ml of saline) in identical volume and subject to the same maneuvers as the intervention on the arm experimental. Participants in the study will be offered the possibility of, once completed the study, receive MSV treatment if it proves beneficial and the patient so wishes. The inclusion criteria in both arms are identical, but after recruiting patients will be randomly assigned to one of the treatments. The Cell manufacturing will be carried out by Citospin at the facilities of the Park Scientist of the UVa and the application and monitoring will be carried out at the Clinical Hospital University of Valladolid. 24 patients diagnosed with low back pain and / or low back pain attributable to disc degeneration and evidence of proven continuity of the external fibrous ring in the magnetic resonance image. The patients will be evaluated clinically, by the previous imaging studies (X-ray and MRI). If they are considered inclusive, they will be provided with the information regarding the clinical trial and the "Patient Information Sheet" (Annex II), citing them for the Inclusion visit. In the "Inclusion Visit", if the patient decides to participate in the trial, they must sign the "Informed Consent Document" and a visit will be scheduled for the practice of MRI and radiographs, which will be considered the pattern on which the possible determinable changes in the controls at 6 and 12 months. If you are MRI and X-rays have been recently performed and their characteristics are valid for the study, its repetition can be avoided. In this visit, basic analytics will also be requested, serology for HIV, lues and hepatitis B and C, and a serum sample will be obtained that will be sent to the Cell Production Unit for filing in the Seroteca. Although the Positive serology is not a criterion for exclusion of the recipient in the present test, it will be performed for epidemiological and preventive purposes. At the next visit (V0), it will be verified that all the inclusion criteria persist and that no exclusion is presented and the patient will be randomized (blind for him) in one of the two treatment groups and the date of implantation of MSV (V1). Once the mobile application is made, the patients will be followed up safety and to determine efficacy as established in the visit program (V2 to V5, see later).

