6.2.2. Randomization numbers

The study population will be made up of 24 patients with low back pain attributable to degenerative disc disease that is refractory to conventional treatment and with integrity of the external annulus fibrosus demonstrated by MR imaging. Of this cohort, 12 patients will be included in the experimental group and another 12 in the control group. Will be assigned to one or the other randomly. It will be carried out by the CRO centrally and at random, attending to the treatment to be administered to each patient (control or experimental). The assignment will be kept in a sealed and identified envelope.

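### The protocol declares double-blind assessment in three places, but section 11.5 defers masking of the researcher and the analysis, and no procedure in the available text settles which holds

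*Combined protocol and SAP*

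**What the plan says.** Three places declare masked assessment. The footnote in the Summary reads: "Double blind, masked for the patient and evaluators performing the analysis of the results, open to the doctor who applies the cells". Section 4.1 carries the same footnote. Section 2.1 adds: "The evaluation of the response to treatment will be blind".

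Section 11.5, on limitations, describes something else. It opens "While the 'single blind' (patient) design is feasible without serious complications" and goes on: "the 'double blind' (researcher) or 'triple' (analysis) various logistical and ethical issues, so they have been left for the future". The sentence has lost a verb, but the deferral is clear.

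On procedure, section 4.2 names one masked party: "the patient will be randomized (blind for him) in one of the two treatment groups". Section 6.2.2 has the CRO randomize centrally and states: "The assignment will be kept in a sealed and identified envelope". Section 3.4 lists "Clinical observations of the surgeon" first among its secondary criteria.

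**The concern.** The masking label governs how every between-arm result will be read. Here the same current text both asserts and defers masking of the people who assess and analyse.

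The measures most exposed carry weight. Disc height and the T2 water-content ratio are the only items under the primary criteria in section 3.3, and quantitative MRI is also part of the main evaluation variable in section 7.1.1. The safety variables in section 11.2.1 count treatment-related serious events, so they depend on a causality judgement. If any of these is made with knowledge of the arm, the trial would be reported with a protection that its own limitations section says was postponed.

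**Working it through.** **Step 1. The masking statements by role.**

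| Role | Summary, 4.1, 2.1 | 11.5 | Other text |
|---|---|---|---|
| Patient | Masked | Masked | 4.2: masked |
| Doctor applying the cells | Open | Deferred, if this is the researcher meant | None |
| Evaluators | Masked | Deferred, if researcher includes them | 4.2 silent; 6.2.2 gives no rule for opening the code |
| Those doing the analysis | Masked | Deferred | None |

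The patient row agrees throughout. The doctor row can be made to agree by reading researcher narrowly. The analysis row cannot: the Summary and section 4.1 mask those who analyse the results, while section 11.5 postpones masking of the analysis. For evaluators the conflict turns on what researcher means.

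**Step 2. Which outcomes are exposed.**

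| Outcome | Section | Who judges | Masking rule in that section |
|---|---|---|---|
| Disc height (mm) | 3.3.1, 11.2.1.1 | Not named | None |
| T2 ratio from ROIs | 3.3.2, 11.2.1.2 | Not named | None in the available text; the Figure 4 legend is not available |
| Signs of regeneration at 12 months | 11.3.7 | Not named; no numerical threshold | None |
| Adverse event causality | 8.2 | Responsible researcher | None |
| Surgeon's observations | 3.4 | Surgeon | None; no analysis in section 11, and 7.1.2 says there are no secondary efficacy variables |
| Pain scale, ODI | Annexes V, VI | Patient | Not needed: the patient is masked in every statement |

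**Step 3. Illustration of size.** The plan gives no effect size, SD or power, so it has no figure of its own to reproduce.

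Inputs from the plan: n = 12 per arm (11.1) and a two-sided 5% level (11.2). Assumed, not in the documents: no true effect, and a reading shift of b SD that favours one arm.

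For a two-sample t-test, df = 2n − 2 = 22 and the noncentrality is b√(n/2) = b√6. The false-positive rate is the probability that a noncentral t variable with these parameters falls outside the two-sided 5% critical values.

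| b (SD) | b√6 | False-positive rate |
|---|---|---|
| 0 | 0 | 5.0% |
| 0.1 | 0.24 | 5.6% |
| 0.2 | 0.49 | 7.6% |
| 0.3 | 0.73 | 10.8% |
| 0.5 | 1.22 | 21.6% |

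This models the between-arm comparison of section 11.2. The imaging subsections themselves name only a paired Wilcoxon test against baseline.

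**The case against.** The strongest reply is that section 11.5 is a loosely worded limitations paragraph that sets no procedure, whereas the design statements say assessment is masked. Its researcher may be only the treating doctor, who is declared open elsewhere too. Central randomization and a sealed envelope give some protection, and section 11.2.1.2 requires the same ROIs at all three times, which limits reader freedom. Efficacy is also preliminary in this trial; the main objective is feasibility and safety.

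Much of this stands. It narrows the evaluator conflict to probable. It does not explain the deferred analysis masking. The envelope protects only if someone controls its opening, and no rule is given. The safety objective does not remove the problem either, because causality grading is itself a judgement.

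A reader might infer more than the documents support:

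- **That section 11.5 says only patient masking is feasible, or that readings will be unmasked.** It says neither; the text leaves the matter open.
- **That ROIs are drawn by hand.** The text does not say so.
- **That the surgeon's impression biases the efficacy result.** It enters no specified analysis, and no section says this surgeon is the doctor who applies the cells.
- **That the questionnaires are equally exposed.** The pain scale and ODI are completed by the masked patient.
- **That the small sample makes this worse.** For a fixed shift in SD units the reverse holds: 0.3 SD gives 10.8% at 12 per arm, but about 32% at 50 and 56% at 100.

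**Conclusion.** The contradiction is real and needs correction. It is certain for the analysis and probable for the evaluators. The available text contains no rule on code custody or coded reading that would settle it, although the missing Figure 4 legend might hold some detail of the MRI reading. Disc height, T2 ratios, the regeneration classification and causality grading may therefore be made with knowledge of the arm; it is not shown that they will be.

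The size cannot be derived from the documents. On the assumed shifts of 0.2 to 0.5 SD the false-positive rate would be about 8% to 22%, and a shift of 0.1 SD would hardly change it. The surgeon's observations are a minor loose end.

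**What to change.** Reconcile the Summary and sections 2.1, 4.1, 4.2 and 11.5 into one masking statement that names who is masked, including for causality grading. In section 6.2.2 say who holds the code.

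In sections 11.2.1.1 and 11.2.1.2 state that the evaluators already declared masked measure disc height and ROIs on images coded without the arm, and that the arm code is released only after the readings are locked.

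If evaluator or analysis masking will not be done, relabel the trial as single blind in the Summary and section 4.1, and correct section 2.1.

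In section 3.4, drop the surgeon's observations as a criterion or limit them to an existing team member masked to arm, and align the section with 7.1.2.

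The cost is protocol wording and the coding of image files, and the surgeon's impression no longer counts as a criterion. No new role is needed if the masked evaluators already declared are in place. If section 11.5 describes the real arrangement, they would have to be arranged or the label changed.
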